Treatment sessions last for 15 minutes (60 trains) with 3000 pulses. The masked randomization status will be maintained for the entire enrollment period, until the last subjects have completed the study in the second year. Cue craving rating and cigarette consumption will be assessed before and after active rTMS or sham rTMS for 10 days. All participants will have two follow-up visits at 1 week and 1 month after the last rTMS session and a follow-up phone after 3 months of the last rTMS session. Safety will be assessed by collecting information on all relevant adverse events experienced.

2. Study Subjects and Entry Criteria Inclusion Criteria: Subjects will:

- (1). Be between the ages of 18 and 60 years old.
- (2) Smoke 10 or more cigarettes per day and have a carbon monoxide (CO) level > 10 ppm indicative of recent smoking.

- (3) Not received substance abuse treatment within the previous 30 days.
- (4) Meet criteria for nicotine dependence as determined by the FTND.
- (5) Be in stable mental and physical health.
- (6) If female, test non-pregnant and use adequate birth control.
- (7) No evidence of focal or diffuse brain lesion on MRI.
- (8) Be willing to provide informed consent.
- (9) Be able to comply with protocol requirements and likely to complete all study procedures.

Exclusion Criteria:

Subjects with:

- (1) Current dependence, defined by DSM-V criteria, on any psychoactive substances other than nicotine or caffeine.
- (2) Contraindication to MRI (e.g., presence of metal in the skull, orbits or intracranial cavity, claustrophobia).
- (3) Contraindication to rTMS (history of neurological disorder or seizure, increased intracranial pressure, brain surgery, or head trauma with loss of consciousness for > 15 minutes, implanted electronic device, metal in the head, or pregnancy).
- (4) History of autoimmune, endocrine, viral, or vascular disorder affecting the brain.
- (5) History or MRI evidence of neurological disorder that would lead to local or diffuse brain lesions or significant physical impairment.
- (6) Unstable cardiac disease, uncontrolled hypertension, severe renal or liver insufficiency, or sleep apnea.
- (7) Life time history of major Axis I disorders such as: Bipolar Affective disorder (BPAD), Schizophrenia, Post-traumatic Stress disorder (PTSD) or Dementia or Major Depression.
- (8) Self report of >21 standard alcohol drinks per week in any week in the 30 days prior to screening.

The baseline evaluation will occur on the same day if the subjects meet the inclusion/exclusion criteria and sign the consent form.

- 1) Demographic Data: Basic demographic information including age, gender, race, and social history will be collected.
- 2) Mini International Neuropsychiatric Interview (MINI) ⁸⁰: This is a well-standardized structured instrument used to provide quick and accurate DSM-IV psychiatric diagnoses. The MINI will be used to confirm the inclusionary/exclusionary diagnoses in the participants.
- 3) Tobacco Use History: Detailed history of current and past tobacco use will be obtained, including cigarette smoking. The questions addressed will include the amount, frequency, duration of smoking, preferred brand, reasons for smoking, smokeless tobacco, family history, etc.
- 4) Fagerstrom Test for Nicotine Dependence (FTND)⁸¹: This is a self-rating questionnaire for nicotine dependence.
- 5) Questionnaire of Smoking Urges- Brief (QSU-B) 82: This is a 10-item self-rating questionnaire for assessment of craving. The questionnaire will be used to track the level of craving during the study. In addition to a total score, the QSU provides scores on two factors: 1) hedonic craving, in anticipation of positive effects, and 2) craving in anticipation of withdrawal relief.
- 6) Beck Depression Inventory II (BDI) ⁸³: BDI is a 21-item self-rating scale to assess symptoms of major depression. We will monitor depressive symptoms during the study due to strong association between smoking and depressive disorders.
- 7) Minnesota Withdrawal Scale Revised (MNWS-R) ⁴: MNWS-R is a DSM-IV based instrument to assess symptoms of nicotine withdrawal.
- 8) Biomarkers: Urine cotinine levels will be used as biomarkers for cigarette smoking. We will use a dipstick urine cotinine (NicAlert, Nymox Pharmaceuticals). NicAlert is a semi-quantitative enzyme linked immunoassay (Elisa test) dipstick measure of salivary or urine cotinine with ranges of 0 10, 10 30, 30 100 ng/ml, etc. The NicAlert dipstick will be done at each study visit. We will also use carbon monoxide (CO) level in the expired air by a standard CO breathalyzer at each visit.
- 9) Tobacco diary: This is a daily diary of all tobacco products consumed in the period between visits, including cigarettes. Participants will maintain a daily tobacco diary, which will be collected at each visit. We have piloted a similar diary in our previous studies. Time-Line Follow-Back is not designed for daily prospective monitoring and hence a tobacco diary will be used.
- 10) Other drug diary: If participant uses marijuana and other drugs, diaries to document other substance use will be provided.
- 11) Modified Cigarette Evaluation Questionnaire- mCEQ: This questionnaire assesses the reinforcing effects of smoking.
- 12) Self Assessment Manikin (SAM) ⁸⁴. SAM is a graphical picture-oriented instrument that can directly assess the pleasure, arousal, and dominance experienced in response to a cue exposure. SAM ranges from a smiling, happy figure to a frowning, unhappy figure when representing the pleasure dimension, and from an excited, wide-eyed figure to a relaxed, sleepy figure for the arousal dimension. The dominance dimension represents changes in control with changes in the size of SAM: a large figure indicates maximum control in the situation. The participants will rate their subjective "happy", "excited", and "control" states.

Table 1. Schedule for data collection

Assessments	Baseline	The 1 st Week TMS	The 2 nd Week TMS	The 1st Follow- up Visit One Week After TMS	The 2 nd Follow- up Visit One Month After TMS	Follow-up Phone Three Months After TMS
Demographic	Х					
Medical history	Х					
Physical exam	Х					
Neuro exam	Х					
MINI	Х					
Psychiatric	х					
evaluation						
Tobacco history	Х					_
FTND	Х	Х	X	Х	Х	Х

QSU-B	Х	Х	Х	Х	Х	
BDI	Х					
MNWS-R	Х					
CO	Х	x daily pre	x daily pre	Х	Х	
Craving rating panel	Х	x daily pre post	x daily pre post			
Tobacco diary	Х	Х	Х	Х	Х	Х
Adverse Events	Х	x daily pre post	x daily pre post	Х	Х	Х
Drug diary	Х					
mCEQ	Х	Х	X	X	Х	
Hematology	Х					
Routine urinalysis	Х					
Urine cotinine	Х	Х	X	X	Х	
Pregnancy test	X					
Urine drug	Х					
MRI scan	Х		TMS Day 10			
Best guess	Х		Х			

- **5. Randomization.** Subjects will be randomized to either sham rTMS over DLPFC or real rTMS over DLPFC with Data Coordination Unit (DCU) at MUSC. Briefly, the subject will be assigned a study number and will then be assigned either a sham or active TMS smart card. An Active Smart Card will only allow TMS treatment with the active TMS head coil. A Sham Smart Card will only work with the sham TMS coil.
- 6. **MRI Scanning Procedures.** At baseline and at the TMS 10 visit, subjects will have a 3.0 T MRI scan of the head with vitamin E tablets placed over the Abductor Pollicis Brevis (APB) motor cortex. Vitamin E tablets are easily visible on the MRI without artifact. We will acquireT1, T2, and FLAIR images to rule out coincidental pathology. These will be followed by high-resolution 3D SPGR images through the whole head (124 contiguous sagittal 0.9 mm slices) for accurate localization.

7. TMS Procedures

- 1). All TMS procedures will be performed by a highly trained faculty or staff member of the Brain Stimulation Laboratory at MUSC under the supervision of a licensed M.D. with specialized training in TMS delivery. All participants will be fitted with a white lycra swim cap at the initial setting. This cap will be worn during the 1st TMS sessions and in the MRI scanner in order to insure proper placement of the TMS coil across visits. The motor cortex will be located and the TMS motor threshold will be assessed. With Brainsight™ neuronavigation software (Rogue Research, Montreal, Canada), the TMS coil will then be moved over the left prefrontal cortex. Using a black permanent marker, landmarks will be placed on the cap to allow for proper refitting for following TMS sessions.
- 2). Treatment parameters and grouping The time in the chair and the number of pulses on the head will be the same for all subjects. Active or sham TMS will be the only difference. The sham group only receives sham at all treatments. Stimulation frequency for all active subjects: 10 Hertz Pulse train duration (on time) 5 seconds, Inter-train interval (off time) 10 seconds (15 second cycle time), Power (intensity) level 100% rMT, Total 60 trains, 15 minutes, Total pulses 3000 per day, 3000 x 10 = 30000 pulses for 10 sessions.

Group 1 = Sham treatment over DLPFC Group 2 = Active treatment over DLPFC

- 3). Treatment Scheduling All participants will be treated Monday Friday for 10 treatments. Ideally, all participants will be treated in the morning, at the same time of day throughout the study, with a note of any time deviation in the case report form (CRF). Each treatment will last about 35 minutes, including 15 minutes of rTMS or sham treatment delivery and 20 minutes pre and post craving rating (10 minutes each). At the end of 5th and 10th rTMS sessions, subjects will be assessed for craving and cigarette consumption.
- 4). Subject Preparation for TMS delivery The subject will be asked to remove and store any glasses or earrings, and to remove wallets from their pockets if they contain magnetic media (e.g., credit cards). They will be asked to empty their bladder to avoid treatment interruption. Ear protection will be provided.
- 5). Resting Motor Threshold (rMT): At entry, we will determine each subject's rMT and all rTMS dosing will be given relative to this value. Surface electromyogram (EMG) will be recorded with silver-silver chloride

electrodes with a tendon-belly arrangement from the APB muscle. The signals will be filtered (band-pass 10 Hz to 1 KHz), amplified, displayed, and stored in a laboratory computer for offline analysis using Signal Software (Cambridge Electronic Design Limited, Cambridge, UK). Resting motor threshold (rMT) will be determined using a Neuronetics® Model 3600 with a solid focal coil TMS machine (Neuronetics, Malvern, PA, USA) by starting with 80% of the machine output and 1 Hz stimulus frequency. The coil will be positioned over the area of the skull roughly corresponding to the motor cortex and then systematically moved and adjusted until each pulse results in isolated movement of the right thumb. Once we completed "threshold hunting", we will use a modified PEST algorithm attached EMG to determine rMT.

- 6). Localizing the TMS Coil over DLPFC: At a visit after providing informed consent, but before the MRI scanning session, participants will be fitted with a white lycra swim cap. This cap will be worn during the MRI scan and during all TMS sessions in order to insure proper placement of the TMS coil across visits. While sitting upright in a comfortable position, the cap will be placed securely over the head, and pulled down to insure an adequate snug fit. Using a black permanent marker, landmarks will be placed on the cap to allow for proper refitting. Localization of the stimulation site in the prefrontal cortex will be performed using Brainsight ™ software along with a brain surface reconstruction. This software allows simultaneous display of high resolution MRIs in the coronal, sagittal and axial planes along with a brain surface reconstruction. Furthermore, after identification of the anterior and posterior commissures, correction for images tilt and limiting the outer brain extension in all planes, the images are normalized to the Talairach coordinate system. First we identify the superior frontal sulcus on the axial images, normally starting with the more superior slices where this sulcus is better displayed. From there, the sulcus is telescoped onto the coronal plane and we select the coronal plane that intercepts the brain 1 cm rostral to the anterior tip of the genu of the corpus callosum. A landmark is picked up on the cortex corresponding to the midpoint of the middle frontal gyrus, and its position is checked on the 3 image planes as well as on the surface reconstruction to confirm that it falls on the middle frontal gyrus. Finally, the Talairach coordinates of the landmark in both the anterior-posterior and dorsal-ventral directions are checked. This landmark, and thus the stimulation site, should lie within the conservative range of Talairach coordinates of Brodmann area 46. Once TMS coil is localized, the location of TMS will be marked on the swim cap and be recorded with the coordinates of Neuronetics chair which will be used for subsequent treatments.
- 7). Treatment administration: The Neuronetics TMS therapy is an FDA-cleared non-invasive medical treatment for patients with major depression who have not benefited from initial antidepressant medication. The Neuronetics TMS device to be used in this study has several important features for this study. First, the TMS coil is iron-filled, and thus does not overheat during repeated stimulation of multiple subjects, as in this clinical trial. Second, Neuronetics has developed a sham coil that looks and sounds much like the real coil, but has a layer of metal between the coil and the brain which blocks magnetic fields from entering the brain. The device also has a rigid arm-holder for positioning the TMS coil on the person's head. Finally, the generator has smart cards, which can be individualized for each subject. Following randomization, each subject will receive a specific card for the treatment. The TMS machine will not work if the wrong coil (real or sham) is attached to the machine for that person. The treatment parameters for an entire 15-minute session can be flexibly programmed. Thus, the intensity of stimulation can gradually be increased over the first minute, which should help with patient tolerability, especially for higher intensity stimulation. Both active and sham treatments will be delivered as programmed into the Smart Card assigned to each subject at the time of the first treatment. The same card will be used each day that the patient returns for treatment.
- 8). Active Sham rTMS: Successful patient and operator masking is key to the success of this trial. In one of our previous studies, we have successfully developed an active sham system ⁴¹. The subject and the treatment operator will be masked to the treatment group assignment, as will all research personnel. Randomization information will be controlled and coordinated through operator 'Smart' cards, distributed by the MUSC CDU. Active sham TMS involves the use of a specially designed sham TMS. The sham TMS system will be connected to an electrical generator on a 9 V battery and electrodes will be placed over the prefrontal cortex. The regulator is triggered by the TMS machine to allow brief, microsecond, pulses of the electrical current through to the skin on the subjects' forehead. Electrical stimulation will be triggered by the TMS machine to correspond to the sham TMS pulses. To further assess the adequacy of the mask, TMS administrators, clinical raters, and patients will complete "best guess" questionnaires, assessing their best guess as to treatment condition, and their level of confidence in this guess.
- 9) Potential problems: (1) *Missed treatment:* Every attempt shall be made to complete each treatment session as per the protocol. Interruptions during the treatment are allowed as needed for patient comfort or

convenience by using the "pause" selection on the device. However, in the event that an incomplete treatment is given, this information will be recorded. In the event that a treatment is missed, the following procedure will be followed: 1 day missed, or 2 days missed in a row—continue into the subsequent week to complete the missed days. Evaluation will still occur after every 5 treatments. 3 or more days in a row—treatment must be aborted and the subject discontinued from their current phase and likely dropped from the study. (2)Monitoring for seizure activity: During the treatment procedure, the treatment administrator must observe the subject closely for any sign of imminent seizure activity or muscle twitching. The administrator must be an individual trained to be perceive to warning signs, and will be familiar with the emergency management of seizure activity. Emergency equipment (oxygen, suction, CPR equipment) will be readily available in the treatment suite. (3)Recording of adverse events: During the treatment procedure, the administrator will assess for and record any adverse events. Prior to leaving the facility following each treatment, the subject will be assessed for the occurrence of adverse events by a qualified individual who is masked to the subject's assigned treatment group. Immediately prior to, and following each TMS treatment session, all patients will complete a Visual Analog Scale to assess within session changes in side effects.

8. Assessments and Instruments (Specific Aim 1 & 3)

- 1). Craving Assessment: Upon arrival at the laboratory, participants will be observed smoking their last cigarette before beginning to complete questionnaires. Immediately prior to, and following each TMS treatment session, all patients will complete a Likert Visual Analog Cue Craving Scale to assess within session changes in subjective craving.
- 2). QSU Brief: Cue presentation and Craving Assessment: Scenic images, neutral control images and cigarette smoking cue images are presented in four blocks. Immediately after viewing each block of cue images, subjects will completed an adapted QSU-B utilizing a computerized visual analog scale (CVAS) designed to assess craving. Each question is followed by a CVAS (the range of 0 and 100).
- 3). Carbon Monoxide: Subjects will be measured CO before TMS daily and at 1 week and 1 month follow-up visits.
- 4). Weekly Assessments: At the end of the 5th and the 10th treatment and 1 week and 1 month follow-up visits, subjects will complete FTND, MNWS-R, Tobacco diary, mCEQ and adverse events.
- 5). At the end of the experiment, subjects will be asked what treatment (active or sham) he/she believes was completed.
- **9. Follow-up (Specific Aim 2).** The treatment period of the study will conclude on the end of two weeks. Participants will then enter the follow-up phase of the study. The two follow-up visits will be scheduled one 1 week and 1 month after the 10th rTMS session. Data will include craving ratings, tobacco diary, CO, QSU-B and FTND. We will conduct a follow-up phone survey of participants 3 months after the 10th treatment. Cigarette consumption will be evaluated by asking: 'How many cigarettes do you now smoke on an average day?'. Craving will be assessed by asking: 'How much do you want to smoke a cigarette right now on a scale from 1 to 10?' and "When was your last cigarette?'. Nicotine dependence will be assessed by the FTND.
- 10. Data Analyses. All data will be analyzed in consultation with Data Coordination Unit (DCU) at MUSC. Quantitative measures of nicotine dependence: Craving rating panel, Tobacco diary, CO, QSU-B and FTND. Side effects: Following standard procedures, frequency and severity measures of side effects will be constructed from the clinical measures. Significance testing: All tests will be two-sided, performed at significance α =0.05, except where noted. The statistical approach will use an ANOVA for each outcome variable. Some data may be longitudinal as well as cross-sectional and we will include random effects to account for within-subject correlation.

Power Analysis. The primary efficacy of rTMS for this study will be the abstinence rate and the number of cigarettes smoked per day at the end of treatment. One previous study of rTMS reported that 10 sessions of rTMS significantly reduced the number of cigarettes per day by the 10^{th} treatment ($18.11 \pm 2.61 \text{ vs.} 10.71 \pm 2.19$) ¹⁹. A power analysis was conducted based upon this two group design, a power of 0.8, and an alpha level of 0.05; a significant difference is anticipated with 18 subjects in each group. The attrition rate in the above mentioned study was 8%. The attrition rate for our previous study was 12% ³¹. According to the attrition

rate from our study (which is more conservative), we will randomize 21 subjects per group (total N=42) to have ample power to detect a clinically meaningful difference. We will use 1 week, 1 month and 3 months follow-up data to calculate power for future R01 studies.

HUMAN SUBJECTS RESEARCH Protection of Human Subjects

- 1. Human Subjects Involvement and Characteristics. Subjects will be women and men aged 18 to 60 years. Subjects meeting inclusion/exclusion criteria (see detail in Study Plan) will be offered participation, regardless of racial/ethnic group. The sample composition will reflect the Charleston-area population distribution of healthy adult smokers.
- 2. Sources of Materials. Research material obtained from the individual subjects will include psychiatric examination results, drug (including nicotine) use assessment results, urine for cotinine levels, expired air breathalyzer alcohol and CO tests, blood samples, heart rate, skin conductance, and subjective ratings (e.g., craving). Urine samples for the urine drug screen and pregnancy will also be obtained. Research data will be obtained specifically for research purposes. We will not use existing specimens, records or data.
- 3. Potential Risks. Investigational Device Exemption: Transcranial Magnetic Stimulation is an investigational device. The IRB at MUSC (in cooperation with the FDA) has determined repetitive TMS to be a non-significant risk intervention.
 - 1). *Potential Risks of TMS:* The major risk using repetitive TMS subjects is the possibility of inducing a seizure. We have now studied and given rTMS to more than several hundred subjects over past 15 years. None of these patients has developed a seizure. We will exclude patients with a prior history of seizures. We have reported that single session doses of 12,960 stimulations were safely given to volunteers with inducing seizures ⁸⁵. We will carefully adjust each person's stimulus intensity to his or her motor threshold, before beginning treatment.
 - 2). Potential hearing loss: The discharge of the rTMS coil generates a high-energy click that may cause cochlear damage. Foam earplugs can protect against these changes and will be worn by the subjects and the researchers present during TMS sessions.
 - 3) Potential risks of active Sham TMS: When subjects receive sham TMS they may experience mild discomfort on their scalp.

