To date, several studies have reported that rTMS reduced cue craving in nicotine dependence ¹⁹⁻²². However, these studies are limited by small sample sizes, variation in stimulation parameters, and in some cases the lack of sham-controlled design and objective measures of tobacco smoking. Furthermore, in all of these studies, stimulation location was targeted to a fixed brain region based on standard skull landmarks. rTMS studies in depression have showed that antidepressant effects are likely depend on coil positioning ^{23, 24}. Personalized coil placement based on a pre-treatment MRI has the potential to enhance outcomes. Additionally the duration or reduced craving following rTMS has yet to be examined. Taken together, while rTMS has demonstrated promise in facilitating smoking cessation, further double-blind investigation is required to determine optimal stimulation parameters and the duration of effect of rTMS in smokers. Furthermore, MRI guided TMS may help us to identify the optimal stimulation location to enhance the effectiveness of the treatment.

This R21 will build on exciting pilot work and advance our knowledge concerning the potential utility of rTMS in smoking cessation by conducting a controlled, double-blind method comparing the impact of ten daily treatments of active rTMS and sham rTMS, on cue-induced craving and cigarette consumption in nicotine-dependent cigarette smokers with extensive monitoring of side effects and smoking outcomes. We propose to directly stimulate the left DLPFC with Brainsight in smokers. In the two years of project, we plan to recruit 42 cigarette males and females of all ethnic and racial groups between the ages of 18 and 60 to participate in the study. Specific Primary Aims include:

Aim 1: To determine under rigorous experimental conditions, whether 10 MRI guided rTMS of left DLPFC treatment sessions over a 2 week period result in superior clinical outcomes compared to sham rTMS in smoking cessation.

Hypothesis 1: We hypothesize that 10 rTMS sessions (15 minutes 10 Hertz active rTMS at 100% resting motor threshold-rMT) over DLPFC will significantly reduce cue-elicited craving and cigarettes per day as compared to sham rTMS.

Aim 2: To evaluate the longevity of clinical benefit of 10 rTMS sessions on smoking measures including cigarettes per day and level of nicotine dependence with following-up 3 months after the last rTMS session.

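### Baseline cigarettes per day is not defined, and the schedule guarantees no diary days before the first stimulation session

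*Combined protocol and SAP*

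**What the plan says.** All references are to the combined protocol and SAP.

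- **Outcome.** The Power Analysis paragraph of section 10 states that primary efficacy "will be the abstinence rate and the number of cigarettes smoked per day at the end of treatment". Hypothesis 1 is that active treatment "will significantly reduce cue-elicited craving and cigarettes per day as compared to sham rTMS".
- **Timing of baseline.** Section 4, Baseline Evaluation: "The baseline evaluation will occur on the same day if the subjects meet the inclusion/exclusion criteria and sign the consent form".
- **Diary.** Section 4, item 9: "This is a daily diary of all tobacco products consumed in the period between visits, including cigarettes". It is collected at each visit. The same item explains the choice of instrument: "Time-Line Follow-Back is not designed for daily prospective monitoring and hence a tobacco diary will be used".
- **Table 1.** The diary row carries the same mark in all six columns, Baseline included.
- **Other smoking data at baseline.** The tobacco history (section 4, item 3) is retrospective: "The questions addressed will include the amount, frequency, duration of smoking, preferred brand, reasons for smoking". Entry requires at least 10 cigarettes a day and expired CO above 10 ppm. CO and urine cotinine are also taken at baseline.
- **During treatment.** Section 8, item 4 lists the diary among the assessments after sessions 5 and 10. Section 10 lists the diary, but not the tobacco history, among the quantitative measures to be analysed.
- **Analysis.** Section 10 names an ANOVA for each outcome, with random effects where data are longitudinal. It names no baseline term. Quality Assurance, in the data and safety monitoring plan, foresees adjustment only if baseline characteristics call for it.

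**The concern.** Section 1 promises that consumption will be assessed both before and after treatment, but nothing says which instrument gives the value before treatment or over how many days. A diary that covers the time between visits cannot hold entries at a baseline that coincides with consent. The plan sets no run-in and no interval before session 1, so the number of diary days before stimulation is left to scheduling and may be nil.

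If so, the baseline figure is recalled and the later figures are daily prospective counts. Any change from baseline then mixes a change in smoking with a change of instrument. Item 9 of section 4 itself treats retrospective and prospective recording as different tools.

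The loss is also permanent. Missing wording can be supplied later in an analysis plan, but diary days that were not recorded before stimulation cannot be recovered.

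**Working it through.** **1. Diary days before session 1.** Call the consent and baseline day 0 and the day of session 1 day g. Complete diary days before stimulation number g − 1. The documents do not state g.

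- Session 1 on the next day: 1 − 1 = 0 days.
- Friday baseline, Monday start: 3 − 1 = 2 days, both at a weekend.
- Seven complete days need g = 8.

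The MRI does not fix g. Section 7, item 6 describes cap fitting at a visit after consent and before the scan, which suggests a gap. The compensation paragraph, however, pays for the baseline MRI as part of the screening visit.

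**2. What an instrument change does.** Let recall be off by a and the diary by b, on average, in both arms.

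- Between arms at end of treatment, diary against diary: (active + b) − (sham + b) = active − sham. The shift cancels.
- Within an arm: (end + b) − (baseline + a) = true change + (b − a). The shift stays in.
- Difference between arms in change: b − a appears in both arms and cancels on average.

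**3. Precision.** Adjusting for a baseline that correlates r with the outcome leaves a fraction 1 − r² of the variance. The documents give no r, so these values are assumptions: 0.7 for a diary baseline and 0.4 to 0.6 for a recalled one.

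- Diary, r = 0.7: 1 − 0.49 = 0.51.
- Recall, r = 0.4: 1 − 0.16 = 0.84; √(0.84/0.51) = 1.28.
- Recall, r = 0.5: 1 − 0.25 = 0.75; √(0.75/0.51) = 1.21.
- Recall, r = 0.6: 1 − 0.36 = 0.64; √(0.64/0.51) = 1.12.

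The standard error is thus 12% to 28% larger with the recalled baseline.

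**4. The same in sample size.** Take the plan's 18 per group as the need of an unadjusted comparison. With a covariate the need is 18(1 − r²): 10 at r = 0.7 (9.2 rounded up), 14 at r = 0.5 (13.5), 17 at r = 0.3 (16.4). With a change score it is 18 × 2(1 − r): 11 at r = 0.7 (10.8), 18 at r = 0.5, 26 at r = 0.3 (25.2). A weak baseline therefore helps little as a covariate, and below r = 0.5 it does harm in a change score.

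**5. The plan's own figures.** The attrition step reproduces: 18/(1 − 0.12) = 20.5, so 21 per group and 42 in all. The 18 does not reproduce if the ± values are standard deviations. The pooled value is √((2.61² + 2.19²)/2) = 2.41 and the difference is 18.11 − 10.71 = 7.40, which needs only 2 per group (normal approximation) or 3 (t-based). If they are standard errors from about 10 to 11 per arm (an assumption), 17 to 19 per group follows. That is a separate matter; neither reading uses a baseline.

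**6. The end of the window.** Section 7, item 3 says: "Ideally, all participants will be treated in the morning, at the same time of day throughout the study". Consumption is assessed at the end of session 10, so that day's count is then incomplete. In an uninterrupted weekday course session 10 falls seven days after session 5, so the last seven complete days begin on the day of session 5.

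**The case against.** The strongest reply has four parts.

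**Baseline smoking is measured.** A reader might infer that there is no measured baseline at all. The documents do not support that: tobacco history, the entry threshold, CO and cotinine are all taken before treatment. What is missing is a statement of which measure is the baseline for cigarettes per day, and any assurance that it is the diary.

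**The primary comparison does not need a baseline.** A reader might infer that the treatment effect is biased. It is not. The plan compares two randomised arms at end of treatment, at the same time and with the same instrument, and names no change score. A reader might also set an assumed recall excess against the 7.40 cigarettes in the power basis. That does not work: the excess is a within-arm artefact, the plan applies the 7.40 to a two-group design, and the text does not make clear whether those two means are between arms or before and after. This part of the reply stands in full.

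**A gap is likely in practice.** MRI is needed both for eligibility and for coil targeting. That is fair, but a likely gap of unknown and varying length is not a defined baseline window, and the compensation text allows the scan on the screening visit.

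**The end-of-treatment data exist.** The diary is daily, complete days before session 10 are available, and smoking later that day falls in the diary collected at the one-week visit. Only the averaging window is missing.

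It is also true that the precision loss is measured against a baseline-adjusted analysis to which the plan does not commit, and that the correlations are assumed.

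**Conclusion.** The point holds in a limited form. Baseline cigarettes per day has no stated instrument or window, and no diary days before treatment are guaranteed. That the outcome values come from the diary is a strong inference from sections 4, 8 and 10, not an explicit statement.

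The between-arm comparison at end of treatment remains valid, and abstinence, the other primary outcome, has no comparable need for a diary baseline. The damage falls on the before-and-after change promised in section 1, on any longitudinal model that includes baseline, and on the precision available from a baseline recorded with the same instrument. On the assumed correlations the standard error is 12% to 28% larger with recall than with a diary baseline. With about 18 evaluable participants per arm, that is worth having.

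The change should be made before enrolment, because the missing days cannot be rebuilt at analysis. It does not put the validity of the main result in doubt.

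**What to change.** 1. Issue the diary at the consent and baseline visit. Require a fixed minimum of complete diary days, for example 7, collected before session 1 and, where possible, before randomisation.
2. Define baseline cigarettes per day as the mean of those days, and name it as a covariate in the analysis of cigarettes per day.
3. Define end-of-treatment cigarettes per day as the mean over a stated number of complete diary days that excludes the day of session 10. A 7-day window reaches back to the day of session 5; a shorter one is noisier but closer to end of treatment. The sponsor should choose and say why.
4. In Table 1, mark the Baseline diary entry as issued and add collection at TMS Day 1.
5. As a complement that causes no delay, ask the average-day consumption question already planned for the three-month call at baseline, after session 10 and at the follow-up visits too. One instrument then spans all time points.

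The cost is protocol wording, about a week between baseline and session 1 (none if scheduling already leaves it), and possibly an occasional drop-out before treatment. Losses before randomisation would not disturb the comparison between arms. No new instrument is needed, and the diary can be collected at session 1, so no extra visit is needed either.
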